Because complete remission is a rare event, one can stipulate that this situation should be a model for studying the pathology of mRCC in response to Sunitinib. It should also permit the sensitivity and resistance to Sunitinib to be explored.

Research is also required to identify markers that can facilitate the screening of patients who would be at low risk of recurrence after complete remission and could potentially benefit from a discontinuation of treatment.

To this end, it is essential to explore the characteristics of the patient at the time of the complete remission compared to those observed at the time of the recurrence, if this occurs, in order to attempt to answer the following questions:

- Is it possible to identify a differential blood marker at the time of the CR compared to the recurrence phase?
- Does one have to distinguish between a CR obtained with medical treatment only and one obtained with the combination of "medical treatment + localized treatment" when, during the retrospective analysis of a series of cases, the 2 cohorts presented the same time to recurrence?
- Can we identify serum or histologic biomarkers that are potentially predictive of a recurrence or CR?
- Is there a correlation between biomarkers identified in patients in CR with Sunitinib compared to patients not in CR with Sunitinib?
- Does the identification of biomarkers help physicians make the decision to stop or continue treatment after obtaining a complete response under sunitinib?

Several biomarkers belonging to different categories, are undergoing investigation because they could reflect the emergence of a resistance or sensitivity to the medicinal product:

- Adhesion molecules (cadherin-6, E-cadherin, MUC1/EMA, ICAM-1, VCAM-1, ELAM- 1, KSA)
- Inducers of immunosuppression (HLA class 1, IL-6, IL-8, IP-10, MIG, MIP1b, B7-H1, B7-H4, CD44)
- Growth factor receptors (VEGFR-3, TGFbR-II, FGFR)
- Hypoxia-inducible factors (CAIX, CAXII, CXCR-4, HIF-1a, VEGF, IGF-I)
- Proliferation markers (Ki-67, PCNA, Ag-NORs)
- Cell cycle regulatory proteins (p53, Bcl-2, PTEN, cyclin A, Akt, p27)
- Analysis of single nucleotide polymorphisms (SNPs) of VEGF and of VEGFRs
- Others (VHL, mTOR, ribosomal protein S6, survivin, IMP3, caveolin-1, PCR, vimentin, fascin, serum amyloid A, NGAL, IGF-1).

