13.11. Appendix 11: Methods for collecting and transporting biological samples

For patients in complete remission (Cases)

- A whole blood sample will be collected during screening visit into two 5 ml EDTA tubes. These samples will be centrifuged and frozen to produce 2 aliquots (minimum) of plasma and 2 pellets of whole blood stored at -80 °C (see diagram below).
- A whole blood sample will be collected during disease progression (if it occurs) into two 5 ml EDTA tubes and processed in the same manner.

For patients screened as controls (2 sites)

- A whole blood sample will be collected before the start of Sunitinib into two 5 ml EDTA tubes and processed in the same manner.
- A whole blood sample will be collected **at 6 months** into two 5 ml EDTA tubes and processed in the same manner.
- A whole blood sample will be collected at 12 months into two 5 ml EDTA tubes and processed in the same manner.
- A whole blood sample will be collected **during disease progression** into two 5 ml EDTA tubes and processed in the same manner.

Storage and transport: These tubes will be stored at -80 °C and transported frozen to the laboratory by OCT Santé, accompanied by the form below.

IGR EXTERNAL SAMPLES HANDOVER FORM

APERÇU

CSET XXXX-XXXX

Investigator: [name]

Consultant CRA: ☎

Sponsor: IGR

Patient identification
(Stick patient label here)

Patient's inclusion/randomization no.:

Enrolling site:

VISIT: Cases

 screening visit PROGRESSION

Or Controls

 Before treatment 6 months 12 months Progression

Sampling date |_____| |_____| |_____| |2|0|1| | _____ Department:

➤ 2 x 5 ml EDTA tubes with "VIOLET" stopper _____ Sampling time: __ :__

[figure not shown]
⇒ Instructions: (gently invert the tubes of blood 6 to 8 times)

Nurse's name and signature:

Comments:

Laboratory services

Comments:

Laboratory services**2 x 5.0 ml EDTA**

**Centrifuge at 2000 g
for 10 min at +4 °C**

**LABELS ON
CRYOTUBES**

**2 aliquots
plasma 1.8 ml
NUNC EDTA
CRYOTUBES**

**2 whole blood pellets
1.8 ml NUNC EDTA
CRYOTUBES**

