13.13 Appendix 13: Sutent – product characteristics summary

Summaries of product characteristics are available at the following links

<http://base-donnees-publique.medicaments.gouv.fr/extrait.php?specid=69225978>

<http://base-donnees-publique.medicaments.gouv.fr/extrait.php?specid=65283820>

<http://base-donnees-publique.medicaments.gouv.fr/extrait.php?specid=63841059>

A printable version will be provided to participating physicians during the implementation of the study.

13.14 Appendix 14: Blood markers of angiogenesis: rationale, parameters analyzed and guidelines Rationale

On the one hand, angiogenesis involves a myriad of angiogenic growth factors and inhibitors synthesized by tumor and stromal cells and, on the other hand, endothelial cells (ECs) and their progenitors. The proliferation of ECs is activated by powerful stimulators, released by tumor cells, vascular endothelial growth factor (VEGF) and basic fibroblast growth factor (bFGF).

It is important to remember that angiogenesis and hemostasis are linked to blood clotting and to fibrinolysis, which directly influence tumor angiogenesis. In fact, activated platelets release numerous angiogenic growth factors such as VEGF, bFGF, SDF-1 and platelet-derived growth factors (PDGFs) and they contribute to tumor angiogenesis within a potentially prothrombotic tumoral microcirculation [1,2].

Angiogenesis markers will be assessed in order to study the role they might play in the prediction of renewed disease progression.

Angiogenesis blood markers analyzed

The plasma levels of the following angiogenic factors will be quantified by ELISA:

- VEGF - prognostic factor of the angiogenesis pathway; target of the antiangiogenic treatment administered.
- bFGF - the levels of which correlate with the prognosis of certain solid tumors and whose proliferative action on endothelial cells is inhibited *in vitro* by
- SDF-1 - synthesized in response to hypoxia. It has a chemoattractive effect on endothelial cells and thus contributes to tumor angiogenesis [3].
- The soluble receptors of VEGF (sVEGFR1 and s VEGFR2), which reduce the angiogenic activity of VEGF.
- The 3 isoforms of PDGF (-AA, -BB and -AB) act on pericytes.

Objectives

- To assess the prognostic value of plasma VEGF in a complete response and progression context
- To study other angiogenesis markers as indicators of a complete tumor response to Sunitinib.

Schedule

The peripheral whole blood collected into EDTA tubes will be tested:

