FOR CASES:

2 x 5 ml EDTA tubes will be collected during the screening visit or during the inclusion visit and in the event of disease progression.

FOR CONTROLS:

2 x 5 ml EDTA tubes will be collected before starting Sunitinib, at 6 months, at 12 months and during disease progression with Sunitinib.

Histological specimens (if available) will be tested:

For cases and for controls:

A histological block or 15 slides of histological sampling of the primary tumor performed before the screening visit.

Guidelines for the sampling, processing, storage and transport of blood samples. The assessment of blood markers of angiogenesis will be centralized at the IGR.

EDTA tubes: assessment of plasma markers of angiogenesis. After 2 rounds of centrifugation at 2000 g at 20 °C for 10 minutes, the plasma will be stored at a temperature of < -20 °C or, preferably, at -80 °C.

Delivery address: Biological Resources Center
Biopathology Department
Institut Gustave Roussy
[name]
[name]
[contact]

References

- 1- Niedrodzik ML & Karpatkin S. Thrombin induces tumor growth, metastasis and angiogenesis: Evidence for a thrombin-regulated dormant tumor phenotype. *Cancer Cell*, 2006;10:355-362.

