2.5 Number of patients required

The primary objective of the study is to describe the characteristics of mRCC patients achieving a CR with Sunitinib (Cases) and to compare them to the characteristics of metastatic renal cell carcinoma patients not achieving a CR with Sunitinib to identify factors associated with the occurrence of complete remission.

A sample size of N = 40 cases and N = 80 controls will provide a power of 80% in the detection:

- For continuous variable with a normal distribution, of an effect size (Cohen's d) ≥ 0.55 ;
- For a dichotomous variable, of a frequency difference between cases and controls corresponding to the ORs presented in the table below:

Frequency in controls	10%	20%	30%	40%	50%	60%	70%	80%	90%
Odds Ratio	≥ 4.33	≥ 3.27	≤ 0.19 or ≥ 3.16	≤ 0.26 or ≥ 3.12	≤ 0.29 or ≥ 3.44	≤ 0.32 or ≥ 3.78	≤ 0.32 or ≥ 5.29	≤ 0.31	≤ 0.23

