4 GENERAL CONSIDERATIONS FOR THE STATISTICAL ANALYSIS OF THE DATA

4.1 Statistical methods

The biostatistics department at AXIAL will perform the statistical analysis, with the exception of the analysis of biological data and biomarkers. Data will be analysed using SAS® software (version 9.4 or later - SAS Institute, North Carolina, USA).

Statistical tests will be carried out bilaterally at a 5% significance level (alpha).

Results will be presented in the form of tables per group (Cases/Controls) presenting:

- For quantitative parameters: number of patients (n), mean and standard deviation, minima and maxima, median and quartiles, and number of missing values.
- For qualitative parameters: number of patients, absolute and relative frequencies for each parameter modality, and number of missing values. Missing data will not be considered when calculating percentages.

Quantitative parameters will be compared between groups using the following methods: Beforehand, the distribution of the parameter will be checked graphically and by using Skewness and Kurtosis and Shapiro-Wilk statistics. If the distribution is considered normal, groups will be compared using a Student's t-test and the difference in means and the 95% Confidence Interval (CI) will be presented. If this is not the case, groups will be compared using a Wilcoxon rank sum test and Hodges-Lehmann estimator, with a presentation of the 95% CI.

For non-ordinal qualitative variables, groups will be compared using the Chi-2 test (or Fisher's exact test if the theoretical numbers <5) and the odds ratio will be presented when specified.

For ordinal qualitative variables, groups will be compared using the Cochran-Mantel-Haenszel test, ridit modified scores ('row mean score differ'). For ordinal qualitative count variables, groups will be compared using the Cochran-Mantel-Haenszel test, 'row mean score differ' table option.

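### No blood-sampling box or handover form records last Sunitinib intake or cycle phase, so plasma-marker differences cannot be reliably separated from drug exposure

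*Protocol*

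**What the plan says.** **Draws.** Appendix 14 of the protocol (Schedule) has Case blood "collected during the screening visit or during the inclusion visit and in the event of disease progression". The Control timetable consists of a baseline draw ahead of treatment, one draw each at months 6 and 12, and a further draw when the disease progresses on Sunitinib. No rule places a draw in the on or off weeks of a 4/2 or 2/1 schedule.

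**Markers.** Appendix 14 lists VEGF, bFGF, SDF-1, sVEGFR1, sVEGFR2 and three PDGF isoforms, all measured in plasma. It describes VEGF as "target of the antiangiogenic treatment administered". Appendix 15 says that Sunitinib acts by inhibiting VEGFR-1 and VEGFR-2.

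**Question.** Section 6 of the protocol asks: "Is it possible to identify a differential blood marker at the time of the CR compared to the recurrence phase". Section 7 adds a comparison of biomarkers between Cases and Controls as a secondary objective.

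**Recording.** Each blood-sampling box in the two case report forms (Appendices 5 and 6) holds a yes/no tick and a date. Under Appendix 11, tubes travel "accompanied by the form below". That form adds visit and clock time.

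**Analysis.** SAP 2.4 assigns biological data and biomarkers to a separate plan, which is not among the documents.

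**The concern.** Cases will be a mixture of patients on and off Sunitinib. Describing who continues and who stops after CR is itself a secondary objective, and the background says that neither course is standardized. A patient sampled on drug in CR and off drug at recurrence has changed both disease state and drug state. A plasma protein that responds to the drug would then differ between the two draws even if it carried no information about recurrence.

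The same applies when Cases of mixed status are compared with Controls at 6 and 12 months, who are mostly on drug. Section 6 also asks whether biomarkers can help physicians decide to stop or continue treatment. A marker that merely reflects stopping would mislead on that question. No later analysis can adjust for exposure that was not captured.

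**Working it through.** **1. What each draw allows.** Sampling boxes set beside the treatment fields in the same case report form:

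| Draw | Treatment information available | On/off status at draw | Cycle phase, last intake |
|---|---|---|---|
| Control, baseline | Sunitinib start date and sampling date; a 6-week delay between initiation and sampling is tolerated | Derivable | Not recorded, and relevant only if drawn after the start |
| Control, 6 and 12 months | Current dose and schedule on the same visit page; no option for stopped | Approximate | Not recorded |
| Control, progression | None on the page; stop date only on the 36-month page | Unreliable, and possibly missing for patients who die or leave earlier | Not recorded |
| Case, CR | Undated continue/discontinue ticks at inclusion; CR may be up to 5 years old | Unreliable; a later annual form may supply a cessation date | Not recorded |
| Case, progression | Months of Sunitinib after CR; restart listed without a start date; annual-form dates where completed | Unreliable; the order of draw and restart is unknown | Not recorded |

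The last column is the firm part of the finding: no form holds either item for any draw.

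**2. The plan's own benchmark.** SAP 2.5 states: "A sample size of N = 40 cases and N = 80 controls will provide a power of 80% in the detection" of a Cohen's d of at least 0.55, with two-sided alpha of 5% (SAP 4.1).

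- Noncentrality = 0.55 x sqrt(40 x 80 / 120) = 0.55 x 5.164 = 2.840.
- Normal approximation: power = Phi(2.840 - 1.960) = 0.811.
- Noncentral t with 118 df: power = 0.804.

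The stated 80% is reproduced. It refers to the primary comparison of patient characteristics, so it serves here only as a yardstick.

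**3. Size of the bias between Cases and on-treatment Controls.** Let s be the shift in a marker between on and off drug, in SD units, and p the difference between groups in the share on drug. With no true difference, the spurious effect is d = s x p. The documents give neither s nor p, so both are assumed and varied. The false-positive rate uses 40 v 80 and the t test above, and assumes that every patient has a usable sample.

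| s (assumed) | p (assumed) | Spurious d | False-positive rate |
|---|---|---|---|
| 0.25 | 0.25 | 0.06 | 6% |
| 0.5 | 1/3 | 0.17 | 14% |
| 0.5 | 0.5 | 0.25 | 25% |
| 1 | 1/3 | 0.33 | 40% |
| 1 | 0.5 | 0.50 | 73% |

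**4. Cycle phase.** On a 4/2 schedule, 2 of 6 weeks are off drug (33%). On 2/1 it is 1 of 3 (33%). If draws are randomly timed and both groups follow similar schedules, the shares cancel: s x (1/3 - 1/3) = 0. The result is extra scatter, not a group difference. Phase produces bias only if schedules or draw timing differ between groups.

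**5. CR against recurrence.** The same product applies within patients, with p the share on drug at the CR draw minus the share on drug at the recurrence draw. The number of recurrences and the within-patient correlation are not given, so no error rate is computed.

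**The case against.** A reader might infer that nothing in the case report forms shows whether a patient was taking Sunitinib, that exposure cannot be separated at all, and that the loss is permanent. The documents do not support any of the three.

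- The Case annual form records ongoing treatment, dose, schedule, interruption and restart dates, and permanent cessation date. The Control 6- and 12-month pages carry dose and schedule with the sampling box. Start and sampling dates settle the Control baseline draw.
- Appendix 14 places the Control progression draw at progression with Sunitinib, which suggests recent exposure, although the form does not confirm it.
- Protocol 8.7 names hospital or physician charts as the usual source documents, and 8.7.1 requires at least 15 years' retention. Chart retrieval is therefore possible.

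Other limits also stand. The separate biomarker plan may stratify or adjust, which cannot be judged here. VEGF and VEGFR polymorphisms are constitutional, so drug status at the draw does not confound them. Pre-Sunitinib Control and in-CR Case samples differ in exposure by design, and no form field removes that. The objectives concerned are secondary, and the shift of up to 1 SD is an assumption.

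The gap in last intake and cycle phase remains, as does the unreliable status at the three draws named above. A biomarker plan can use only what was captured or can be retrieved.

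**Conclusion.** The point holds for the plasma angiogenesis proteins. Last intake and cycle phase are recorded for no draw, and on/off status is unreliable for the Case CR draw and for the progression draws in both groups. Differences between CR and recurrence, and between Cases and on-treatment Controls, cannot be reliably separated from drug exposure.

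The size is unknown. Over the assumed range it is about 0.06 to 0.5 SD. The upper end approaches the 0.55 SD yardstick, but it requires both a 1 SD drug effect and a 50-point imbalance in on-drug share. The lower end is negligible, with a 6% false-positive rate against the nominal 5%. The primary comparison of patient characteristics is not touched. The change is worth making because it is cheap and the information becomes harder to recover with time.

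**What to change.** 1. Add two items to the Appendix 11 handover form and to every blood-sampling box in Appendices 5 and 6: Sunitinib status at the draw (not yet started / on phase / off phase / temporarily stopped / permanently stopped) and date of last intake. Leave the timing of draws unchanged.
2. For samples already banked, retrieve both items from charts where available, and flag those that cannot be recovered.
3. In the separate biomarker plan, report plasma-marker comparisons adjusted for or stratified by Sunitinib status beside the pooled comparison. State that differences between pre-Sunitinib Control and in-CR Case samples will not be attributed to CR alone. Constitutional polymorphisms need no such adjustment.

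The cost is two fields per draw, some chart work at sites, and some last-intake dates that will stay missing. With at most 40 Cases the strata will be small, so stratified estimates will be imprecise; this is why the pooled result should be kept beside them.

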13.15 Appendix 15: Analysis of genetic polymorphisms

Rationale

The isoforms of VEGF-A are encoded by a single gene at locus 6p12. Although no polymorphisms have been identified in the coding regions, several allelic polymorphisms located in the promoter region 5' of exon 1 or in the UTR region of exon 8 may explain the variations between individuals in the production of VEGF (1). It has been reported that significant variations in the blood levels of VEGF during hypoxia or during coagulation disorders correlate with polymorphisms (2, 3). Given the important pathophysiological role of angiogenesis in the development of clear cell carcinomas, it will be interesting to see whether these polymorphisms correlate with the occurrence of a complete response.

Sunitinib is an active treatment of renal cell carcinoma that acts by inhibition of the tyrosine kinases of VEGFR-1 and 2. Because elevated blood levels of VEGF, as well as significant quantities of VEGF bound to the extracellular matrix, can influence the efficacy of Sunitinib, it will also be interesting to examine the link between constitutional polymorphisms of VEGF and the occurrence of a complete response with Sunitinib.

Due to interference with one of the strongest targets of Sunitinib, VEGFR-2, polymorphisms may also perturb the level of response.

Polymorphisms analyzed

The non-exhaustive list of the polymorphisms that will be analyzed includes the analysis of the polymorphisms of the different VEGFRs and VEGF. The analysis of polymorphisms will be done by DNA sequencing after PCR amplification. The assessment of polymorphisms will be done at the end of the study.

Guidelines for the sampling, processing, storage and transport of blood samples.

2 EDTA tubes containing 5 ml samples (see Appendices 10 and 12) will produce 2 pellets of whole blood and allow the extraction of DNA for analysis of polymorphisms.

Delivery address:

Biological Resources Center
Institut Gustave Roussy
[name]
[name]

References

1 INTRODUCTION

This Statistical Analysis Plan (SAP) presents the definitions used for the efficacy and safety endpoints as well as the analysis sets. It also describes the data derived and indicates the statistical methods used.

This SAP is based on amended version no. 5 of the protocol dated 21/11/2017.

The analyses comply with the guidelines of the ICH industry standards (E3 - Structure and Content of Clinical Study Reports and E9 - Statistical Principles for Clinical Trials).

2 DESCRIPTION OF THE STUDY

2.1 Rationale

Complete remission (CR) is a rare event in metastatic renal cell carcinoma (mRCC) treated with tyrosine kinase inhibitors; however, findings from two retrospective cohorts report that it occurs in 1-2% of patients treated with Sunitinib.

CR when taking Sunitinib has been described in the different prognostic subgroups and has also been reported in cases of multiple metastases. A series of reports also suggest that significant objective responses are achievable in a sub-population of patients receiving targeted therapy, and that complete residual metastasectomy may be beneficial in well-selected patients having presented a partial response to anti-angiogenic therapy.

No standardised management has been established for the continuation or discontinuation of treatment in patients achieving a complete remission with Sunitinib.

In addition, therapies targeting Vascular Endothelial Growth Factor (VEGF) have been associated with the development of resistance after 6-15 months of treatment. Sequential use of these molecules has become standard practice. In fact, activity is observed with an agent with the same or some common targets as one of the previous treatments and for which disease progression had been observed. This raises questions about resistance mechanism(s) and the optimal therapeutic approach in this context. However, it appears that this resistance is potentially reversible. In a retrospective review of mRCC patients treated with Sunitinib after disease progression following previous therapy with Sunitinib and other treatments, the reintroduction of Sunitinib was effective and well tolerated in most cases.

In CR patients receiving targeted therapy alone or in combination and an additional metastasectomy, one case series showed that in almost 50% of cases discontinuation of Sunitinib was followed by recurrence but that reintroduction of targeted therapy was effective in most cases.

Improving the characterisation of patients achieving a CR with Sunitinib is therefore necessary to provide doctors with information about the appropriate approach in such cases and to encourage surgeons to operate on patients with a single or minimal residual metastases.

The analysis of CR patients should compare these rare cases to the more common situation of patients treated with Sunitinib but who do not have a complete response. Given the rarity of the event being studied, it is proposed that the design of the study should be a case-control study.

